8.1 Description of planned statistical methods, including schedule of planned interim analysis

8.1.1Descriptive analysis

A first overall descriptive analysis and analysis by group will be performed. This consists of separate estimates, numbers and percentages for qualitative variables, means, standard error, medians and interquartile intervals for quantitative variables. The normal feature of the distribution of quantitative variables will be checked (Shapiro test).

8.1.2Comparison of groups at inclusion

Student's t test or a Mann-Whitney test if necessary will be used to compare quantitative variables, and a Chi² or Fisher's exact test if necessary will be used to compare qualitative variables between two groups at inclusion.

8.1.3Analysis of the primary criteria

The primary endpoint (rate of nosocomial infection at day-28 after CPB) will be compared between the two groups with the Chi²test.

Two interim analyses after inclusion of 1/3 and 2/3 of the patients, and one final analysis are planned. Stopping rules will use the alpha spending function with the O'Brien-Fleming boundary. The cumulative values of alpha for each analysis are: 0.00021 at the first analysis, 0.01202 at the second analysis and 0.04626 at the final analysis (nTerim, V1.1, Statistical solutions Ltd, Cork, Ireland). The trial will be stopped early if the significance of the Chi² test is below these alpha values.

8.1.4Analysis of other criteria

For the analysis of the other endpoints, the same strategy as for baseline comparisons will be used.

In addition, censored endpoints (survival) will be compared using the log-rank test.

Continuous endpoints repeatedly measured during the study will be compared using a repeated measure two-way (time, group) analysis of variance.

For all these analyses, adjustments can be made in case of heterogeneity at inclusion.

8.1.5Analysis of adverse events

Possible adverse events are coded according to the MedDRA classification and are the patient of a descriptive analysis.

8.2 Planned number of persons to be enrolled in the study, and planned number of persons in each centre with its statistical justification

Our hypothesis is that 15% of the patients without MV during CPB (MV- group) will have post-operative infection at day 28. A total sample size of 1392 patients (696 per group) is required to achieve 80% power to detect a decrease in the rate of postoperative infection in patients with MV during CPB (MV+ group) to 10%, using a two-sided test with a type I error of 5% (nTerim, V4.0, Statistical solutions Ltd, Cork, Ireland), **1400 will be included to take into account potential non evaluable patients (death during surgery, lost to follow-up...).**

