Infections are the most common non-cardiac complication after cardiac surgery. Infection in the setting of cardiac surgery increases morbidity, mortality, and cost. These infections can require prolonged treatment with antibiotics, additional surgery, or both. Several studies have found that 15-20% of patients will experience postoperative infections. In a recent prospective study, 15% of patients developed postoperative infections which dramatically affected survival and readmissions (23-26). The authors found that prolonged ventilation and transfusion were associated with adverse outcomes and emphasized the considerable opportunities for improving outcomes and preventing postoperative infection. However, no pharmacological strategies have reduced this immunosuppression (gluccorticoids, protease inhibitors, heparin, phosphodiesterase inhibitors, antioxidants...) (5, 18, 19, 25, 27-31). In a prospective, randomized, double-blind, placebo-controlled study, Tepaske et al. aimed to ascertain whether oral immune-enhancing nutritional supplement taken for at least 5 days before an operation in high-risk patients undergoing cardiac surgery improves preoperative host defense and subsequently reduces postoperative infections and organ dysfunction. They demonstrated that CPB decreased dramatically HLA-DR expression on monocytes in both group. However they found that concentration of IL-6 was significantly lower in the treatment group than in the control group (5). Although these results are interesting, no study has demonstrated that its finding could be generalized to other patients.

Cardiopulmonary bypass during cardiac surgery promotes inflammatory response and immune dysfunction that increase the occurrence of postoperative infection. Reducing postoperative inflammation will decrease postoperative immunosuppression and therefore will decrease patient morbidity.

B. Cardiopulmonary bypass induced pulmonary dysfunction

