4.3 Description of the measures taken to reduce and prevent bias

4.3.1 Randomization

Randomization will be stratified per centre.

Randomization will be performed in the centres via a webinterface (Ennov Clinical, Ennov Group, Paris, France). A document to help use this tool will be provided to the investigators.

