11.2 Substantial changes

In case of a substantial change made to the study protocol by the investigator, it will be approved by the sponsor. The latter must obtain prior to start of study a favourable opinion from the ethics committee and authorisation from the relevant health authority in the setting of their respective competence. Additional consent from persons participating in the study will be collected if necessary.

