14 STUDY FEASIBILITY

Two smaller scale studies (pilot studies) have been already conducted to test the plan and method of this research study with convincing results (Appendixes 4-5-6).

Eligibility criteria and study design will not hinder enrollment expectations. With 7 centers (almost 10 000 CPB/years) enrollment goals will be achieved.

There are no known open competing studies registered to *clinicaltrials.gov* (September 2016).

Study plan does not conflict with currently accepted practice.

Study has been found to be of great scientific interest among potential co-investigators in surgery, anesthesiology and intensivist.

This study has been endorsed by the REVA network (Appendix 8).

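### The primary Chi² test and the stopping rule leave out centre, the randomisation factor; a centre-stratified test would be a small, optional gain in efficiency

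*Combined protocol and SAP*

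**What the plan says.** Section 4.3.1 names one stratification factor: "Randomization will be stratified per centre". Section 14 gives the number of sites: "With 7 centers (almost 10 000 CPB/years) enrollment goals will be achieved".

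Section 8.1.3 sets the primary analysis: "The primary endpoint (rate of nosocomial infection at day-28 after CPB) will be compared between the two groups with the Chi²test". The same unstratified statistic drives early stopping: "The trial will be stopped early if the significance of the Chi² test is below these alpha values". Neither sentence has a centre term.

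The only wording on adjustment is in section 8.1.4, which deals with the other endpoints: "For all these analyses, adjustments can be made in case of heterogeneity at inclusion". It is optional, depends on imbalance at baseline and does not name centre, so it does not bring centre into the primary test.

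**The concern.** The usual practice is to analyse by the factors used to randomise. If infection rates differ between centres and the arms are balanced within each centre, part of the outcome variation is variation between centres that cannot bias the comparison. The plain Chi² test still counts that variation as noise. It is then slightly conservative and gives up a little power, at the interim looks as well as at the end.

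What is at stake is efficiency, not validity. The question is whether the gain is large enough to be worth a change to the plan.

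**Working it through.** **Inputs from the documents**
- Control rate 15%: "Our hypothesis is that 15% of the patients without MV during CPB (MV- group) will have post-operative infection at day 28". Target rate in the ventilated arm 10%, two-sided 5%, 80% power, 1392 patients (696 per group), 1400 to be included (section 8.2).
- Looks at one third, two thirds and all patients, with alpha values 0.00021, 0.01202 and 0.04626 (section 8.1.3).
- Seven centres (section 14).

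**Step 1: reproduce the plan's sample size.** For a fixed design with the pooled-variance formula:

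n per arm = [1.960 × √(2 × 0.125 × 0.875) + 0.842 × √(0.15 × 0.85 + 0.10 × 0.90)]² / 0.05² = (0.917 + 0.393)² / 0.0025 ≈ 686, or 1372 in total.

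With the three looks, and the stated alpha values used as p-value thresholds at each look, 696 per arm gives 80.0% power (pooled variance) to 80.2% (unpooled). The overall type I error is 4.99%. So 1392 is the group-sequential figure, and it reproduces.

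**Step 2: choose centre rates.** The documents give no rates, sizes or block size by centre. The only spread they report is between studies, not centres: "Several studies have found that 15-20% of patients will experience postoperative infections". Four sets of seven equally spaced control rates averaging 15% are therefore assumed: all 15%, 12.5-17.5%, 10-20% and 5-25%. The second has the same width as the reported between-study range.

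**Step 3: variance formula.** With equal centres balanced within centre, the true variance of the difference under no effect, relative to what the Chi² test assumes, is

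ratio = mean[p_c(1 − p_c)] / [p̄(1 − p̄)] = 1 − Var(p_c) / [p̄(1 − p̄)].

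For 5-25%, the spacing is 20/6 = 3.33 points. The variance is 3.33² × (7² − 1)/12 = 44.4 squared points = 0.00444, so the ratio is 1 − 0.00444/0.1275 = 0.9651. The four ratios are 1.0000, 0.9978, 0.9913 and 0.9651.

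For a single look at 0.04626 (z = 1.993), the true size is 2[1 − Φ(1.993/√ratio)] = 4.63%, 4.60%, 4.53% and 4.25%.

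**Step 4: simulation over all three looks.** Each setting used 300,000 trials, 700 per arm and a common odds ratio (0.630, 0.629, 0.627, 0.621) set to give 10% overall in the ventilated arm. The pooled Chi² was compared with the Cochran-Mantel-Haenszel test, both without continuity correction. The power and size rows are for seven equal centres with arms balanced within centre.

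| Control rates by centre | 15% everywhere | 12.5-17.5% | 10-20% | 5-25% |
|---|---|---|---|---|
| Power, Chi² (%) | 80.6 | 80.6 | 80.7 | 81.0 |
| Power, stratified (%) | 80.6 | 80.6 | 80.8 | 81.8 |
| Gain, balanced within centre (points) | -0.055 | +0.008 | +0.177 | +0.761 |
| Gain, centres of 5% to 30% of patients, balanced (points) | -0.046 | +0.016 | +0.144 | +0.698 |
| Gain, equal centres, no balance within centre (points) | -0.198 | -0.141 | +0.111 | +0.983 |
| Size, Chi² (%) | 5.1 | 5.0 | 4.9 | 4.6 |
| Size, stratified (%) | 5.0 | 5.0 | 5.0 | 5.0 |

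The paired standard error of the gains is 0.006 to 0.016 points for equal balanced centres and 0.022 to 0.037 with no balance. Each size has a standard error of 0.04 points, so differences below about 0.1 point are noise, including the 5.1%. With no balance within centre the Chi² is not conservative: its size is 5.0, 5.0, 4.9 and 5.0%.

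**Step 5: check with other centre rates.** A separate simulation (200,000 trials per setting) used a non-linear spread of rates described by the between-centre standard deviation (SD). The gain was 0 to 0.1 point at an SD of 3 points or less, about 0.5 at 5, 1.0 at 7.5, 1.8 at 10 (control rates 4-35%) and 4.2 at 15 (1-47%). The 5-25% setting above has an SD of √44.4 = 6.7 points. Its gain of 0.8 falls between the values for 5 and 7.5, as it should.

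**The case against.** The strongest case against raising this is that nothing is wrong. A prespecified Chi² test with nominal or slightly conservative size and about 80% power does what section 8.2 asks. Section 4.3.1 describes allocation and does not promise a stratified analysis. With centres alike or at 12.5-17.5%, the gain is indistinguishable from zero or slightly negative; a gain near one point needs a fivefold spread of control rates. At 12.5-17.5%, the variance ratio is worth about 0.0022 × 1392 ≈ 3 patients. Against that stands a rewrite of the primary test and stopping rule, possibly through ethics and health-authority review.

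Most of this stands. It shows that the point is an improvement and not a correction, and that the benefit rests on centre differences the documents do not quantify. It does not remove the point. The analysis does leave out the one factor that the design uses, no other text supplies it, and the possible loss (at most about 0.2 point) is smaller than the possible gain (up to about 1 point in the main settings). Which case applies cannot be known beforehand.

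Two further objections concern detail. A stratified risk difference needs stated weights and a confidence level. The alpha values are labelled cumulative although they behave as per-look levels. Both deserve attention in any edit of section 8.1.3, but neither weakens the case for the stratified test.

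**Conclusion.** The point holds as a minor, optional improvement. The primary test and the stopping rule omit centre. The Chi² test remains valid, its type I error is not inflated, and power stays at about 80%.

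Stratifying by centre changes power by roughly -0.2 to +0.2 points for control rates spanning up to 10-20%, and by +0.7 to +1.0 at 5-25%. Gains above that need wider spreads still.

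These figures assume seven centres, a common odds ratio, the stated alpha values used as per-look thresholds, and invented centre rates. The conservatism of the Chi² test also depends on balance within centre, and no block size is given.

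**What to change.** In section 8.1.3, replace the primary-test sentence with wording such as:

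*The 28-day nosocomial infection rate in the two arms will be tested with a Cochran-Mantel-Haenszel test stratified by centre, at each interim analysis and at the final analysis. The centre-stratified risk difference (Mantel-Haenszel weights) will be reported with its confidence interval.*

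State the confidence level in the same sentence. In the stopping sentence, replace the Chi² test with the Cochran-Mantel-Haenszel test. The sample size, the timing of the looks and the alpha values stay as they are. The choice should be fixed before the first interim look.

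The change needs no new patients, data or case-report-form items. If centres prove alike, it costs about 0.1 point of power with arms balanced within centre, and about 0.2 with no balance at all. The real cost is procedural. Section 8.1.3 is protocol text that sets the stopping rule, so the change may count as substantial under section 11.2: "In case of a substantial change made to the study protocol by the investigator, it will be approved by the sponsor". That section also requires an ethics committee opinion and health-authority authorisation. The gain hardly justifies an amendment on its own; it is best made if section 8.1.3 is being amended anyway, for example to clarify the cumulative label on the alpha values.

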4.2.2.2. Inclusion phase

The patients will be randomized the day of surgery before induction of anesthesia.

Data collected at inclusion: The following data were collected: age, sex male, body mass index (BMI), EuroScore, type of surgery (isolated coronary artery bypass graft (CABG), single valve, surgery on multiple valve, CABG plus valve), coexisting medical conditions (Hypertension, diabetes mellitus, previous cerebrovascular event (stroke/transient ischemic attack), peripheral vascular disease, preoperative creatinine, chronic renal dysfunction), antibiotic prophylaxis.

Description of surgery:

- General anesthesia will be induced with propofol and sufentanil (or remifentanil) and will be followed by cisatracurium for muscular relaxation. Anesthesia, muscle relaxation, and analgesia will be respectively maintained with inhaled sevoflurane during off-pump surgery or propofol infusion during CPB and boluses of atracurium and sufentanil (or remifentanil).
- For baseline ventilation, the patients will receive volume-controlled ventilation with a tidal volume of 6-8 mL/kg of predicted body weight and a ventilatory frequency of 10 to 15 per minute (end-tidal carbon dioxide between 34 and 38 mmHg). Inspired oxygen fraction (FIO2) will be adjusted to ensure a peripheral oxygen saturation of > 92%, inhalation-to-exhalation ratio will be 1:2, and the level of PEEP will be 5-7 cmH2O.
- During CPB, two settings will be used depending on the study arm:
 - In the control group (MV- group): absence of MV (and no PEEP) by disconnecting the tracheal tube from the ventilator;
 - In the MV + group: dead space ventilation using tidal volume of 2.5 mL/kg/pbw (predicted body weight) with 5-7 cmH2O PEEP.
- After CPB, a recruitment maneuver will be performed. Recruitment maneuver consisted of applying a continuous positive airway pressure of 30 cm of water for 30 seconds, and then ventilatory parameters will be turned back to

baseline settings. All postoperative patients will be admitted to the intensive care unit (ICU) and will be ventilated with volume-controlled ventilation, VT=6-8 ml/Kg/pbw, FiO2 of 60% and PEEP of 5cmH2O.

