5 SCREENING AND INCLUSION OF PERSONS FROM THE STUDY

5.1 Inclusion criteria

- Age \geq 18 years old;
- Scheduled for any cardiac surgery (elective surgery) with cardio-pulmonary bypass, aortic clamp and cardioplegia, with median sternotomy and bi-pulmonary ventilation (cardiac valvular surgery (valve replacement or repair), coronary artery surgery, ascending aortic surgery and/or combined);
- Written informed consent.

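### The unadjusted primary Chi² test is valid and reaches its planned 80% power, but it leaves the risk variables recorded at inclusion unused; separately, the surgery-type list has no entry for ascending aortic surgery

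*Combined protocol and SAP*

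**What the plan says.** Section 8.1.3 sets the primary analysis: "The primary endpoint (rate of nosocomial infection at day-28 after CPB) will be compared between the two groups with the" Chi² test. The two interim looks and the final look apply their significance limits to that same test. No covariate enters it, and neither does centre, although section 4.3.1 stratifies randomisation by centre.

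Section 8.2 gives the basis of the design: "Our hypothesis is that 15% of the patients without MV during CPB (MV- group) will have post-operative infection at day 28", against 10% with ventilation. It continues: "A total sample size of 1392 patients (696 per group) is required to achieve 80% power". The reserve is small: "1400 will be included to take into account potential non evaluable patients", that is, 8 more than 1392.

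Section 4.2.2.2 lists what is recorded at inclusion. The list includes EuroScore, diabetes and "type of surgery (isolated coronary artery bypass graft (CABG), single valve, surgery on multiple valve, CABG plus valve". Section 5.1 admits "coronary artery surgery, ascending aortic surgery and/or combined" procedures as well as valve surgery.

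Two other clauses bear on the point. Section 8.1.4, on the other endpoints, permits adjustment if the groups turn out to differ at baseline. Section 8.4 says that missing values are left unreplaced.

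**The concern.** Adjusting a randomised comparison for baseline variables that predict the outcome narrows the standard error, and a standardised risk difference does so without changing the question. The variables are already collected, so the extra precision needs no new measurement and no extra patients. With a design set at 80% power and an allowance of 8 patients, even a modest gain is worth having.

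The clause in section 8.1.4 is not a substitute. If it were read as reaching the primary endpoint, whether to adjust, and for what, would be decided after the baseline tests of section 8.1.2 had been seen. Naming the covariates in advance gains the precision and closes that choice.

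The surgery-type list raises a separate, smaller point. An admitted procedure has no entry in it, and type of surgery is one of the natural adjustment variables.

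**Working it through.** **1. Reproduce the sample size.** Inputs from section 8.2: rates 0.15 and 0.10, two-sided 5%, 80% power. Mean rate 0.125.

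n per arm = [1.960 × √(2 × 0.125 × 0.875) + 0.8416 × √(0.15 × 0.85 + 0.10 × 0.90)]² / 0.05² = (0.9167 + 0.3925)² / 0.0025 = 686, or 1372 in total.

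O'Brien-Fleming-type spending at 1/3, 2/3 and 1 gives per-look p-values of 0.00021, 0.01202 and 0.04626, the values in section 8.1.3. These looks inflate the sample size by 1.0128: 686 × 1.0128 = 695 per arm, 1390 in total, against 1392 stated. Group-sequential power at 696 per arm is 80.1%. The unadjusted test therefore delivers what section 8.2 promises.

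**2. Gain from adjustment.** The documents do not say how well the inclusion variables predict infection, so the c-statistic is an assumption. Model: one normally distributed risk score, linear on the logit scale, with marginal rates held at 15% and 10%. The ratio is the variance of the standardised risk difference divided by that of the raw difference. Extra patients = 1392 × (1/ratio − 1). For power, the expected z-value is divided by √ratio and run through the three looks.

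| Assumed c-statistic | Variance ratio | Worth in patients | Power (from 80.1%) |
|---|---|---|---|
| 0.55 | 0.9965 | 5 | 80.2% |
| 0.61 | 0.982 | 25 | 80.8% |
| 0.65 | 0.966 | 49 | 81.4% |
| 0.70 | 0.936 | 95 | 82.6% |

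A separate calculation gave ratios of 0.967 and 0.939 at 0.65 and 0.70, hence 47 and 90 patients, so the last two rows are best read as 47–49 and 90–96. A fixed-design simulation (696 per arm, 6000 runs per scenario) of the Chi² test against adjusted logistic regression points the same way: 80.3% and 80.3% at 0.55, 80.9% and 82.1% at 0.65, 81.0% and 83.3% at 0.70. The table uses large-sample formulas and ignores the small cost of estimating the coefficients.

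**3. Sensitivity to missing covariates.** If section 8.4 is applied literally, an adjusted model drops every patient who lacks a covariate; the Chi² test drops none of them. At a c-statistic of 0.61 the gain is 25/1392 = 1.8%, so about 2% incomplete covariates would cancel it.

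**4. Estimand.** In these scenarios the conditional odds ratio from a logistic model moves from 0.63 to 0.60 as the c-statistic rises from 0.55 to 0.75, against a marginal odds ratio of 0.63. A standardised risk difference keeps the 15% against 10% contrast of section 8.2.

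**5. Surgery types side by side.** Section 5.1 admits valve, coronary and ascending aortic surgery, and combinations. Section 4.2.2.2 lists isolated coronary bypass, single valve, multiple valve, and bypass plus valve. Ascending aortic surgery, alone or combined, fits none of the four. The documents do not give its share of cases. If it were 5–10% (assumption), that would be 0.05 × 1400 = 70 to 0.10 × 1400 = 140 patients.

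**The case against.** The strongest reply is that nothing here is an error. The Chi² test is valid under randomisation, matches the sample-size basis and is easy to explain, and preferring it is legitimate. That stands. A reader might infer that the trial loses power it was counting on. The documents do not support this, because the stated 80% already assumes the unadjusted test.

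The second objection is that the gain rests on an unstated premise. The documents do not say that EuroScore, type of surgery or diabetes predicts infection in this population. The background in section 2.1 names prolonged ventilation and transfusion, neither of which is an inclusion variable. The exclusions in section 5.2 may also narrow the spread of risk. This stands too, and is why the range starts at 0.55, where the gain is 5 patients.

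The third is that adjustment has costs. In a fixed-sample simulation with 3% missing covariates and an assumed covariate mix, dropping incomplete patients left about 79% power at 0.61 and 80% at 0.65, against 79–80% for the Chi² test: no clear gain. This stands against an adjusted model without a missing-covariate rule, and is met by writing one. Centre, the stratification factor, also belongs in the model.

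On the surgery list, a reader might infer that aortic patients are misclassified. That is not shown. The list is a protocol summary, and the e-CRF, which may hold an aortic or other code, is not in the documents.

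**Conclusion.** This is a worthwhile improvement, not a flaw. The primary test is valid and adequately powered as planned. Pre-specified adjustment would add about 0.1 to 2.5 points of power over assumed c-statistics of 0.55 to 0.70. The benefit depends on a prognostic strength that the documents do not give, and on keeping patients with incomplete covariates in the analysis. The clause in section 8.1.4 does not provide it.

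The surgery-type gap is a mismatch between sections 4.2.2.2 and 5.1. Only if the e-CRF follows the protocol list would aortic patients be uncoded or placed in a wrong category, and then only the baseline table and adjusted analyses would suffer. Type of surgery does not enter the planned Chi² test.

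**What to change.** In section 8.1.3:

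- Make the primary test the standardised (marginal) risk difference from a logistic model with arm, centre, EuroScore, type of surgery and diabetes, with a robust standard error.
- Compare its z-statistic with the stated boundaries at all three looks, and keep the Chi² test as a sensitivity analysis.
- State that patients with a missing baseline covariate are kept, for example by single imputation or a missing category, done without regard to arm. Cross-refer to section 8.4 so that its rule does not drop them.
- State a fallback in case the model does not converge at the first look. With about 1392/3 = 464 patients and a mean rate of 12.5%, about 58 infections are expected. The model would have 13 coefficients besides the intercept: arm 1, the seven centres of section 14 give 6, EuroScore 1, five surgery types give 4, diabetes 1.

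In section 4.2.2.2, add a category for ascending aortic surgery, alone or combined, and check that the e-CRF carries it.

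The cost is SAP wording, a few lines of code and at most one e-CRF category, with no new measurement and no extra patients. The downside is a primary analysis slightly less simple than a two-by-two table.

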4.2.2.3. Follow-up

Data collected after surgery: duration of procedure, duration of CPB, duration of aortic cross-clamping, antibiotics treatments, duration of MV, length of stay in ICU, hospital length of stay, mortality.

Immunomonitoring parameters (HLA-DR expression, IL-10 and IL-6, lymphocytes count, Indoleamine 2,3-Dioxygenase activity, MDSCs and EV) will be obtained after general anesthesia and before surgery (D0, at 24 hours (D1) and 7 days (D7) (except EV) after surgery.

HLA-DR expression, IL-10, IL-6 and IDO activity will be measured in Rennes.

Ratio of arterial oxygen tension (PaO2) to FIO2 will be obtained before surgery (D0) after induction of anesthesia and 3 h after the end of CPB in the surgical intensive care unit (ICU; under baseline MV settings), and the day after surgery (D1).

Occurrence of postoperative infections within 28 days following cardiac surgery will be monitored. An independent committee blinded to treatment group will ensure the classification of hospital-acquired infections. Antibiotics treatment, length of stay, duration of MV, mortality will be recorded within the first 28 days following surgery.

	Screening Phase	Inclusion Phase (D0) Surgery	D1	D7	D28
Information document	Х				
Clinical Examination (check the selection criteria)	X				
Written informed consent	Х	Or X (later)			
Randomization		Х			
Patient characteristics and clinical data		Х			
Data surgery		Х			
HLA-DR* and MDSCs*		Х	Х	Х	
IL-10*		Х	Х	Х	
IL-6*		Х	Х	Х	
IDO activity*		Х	X	X	

EV*	Х	X		
Lymphocytes count	Х	X	X	
Pa02/Fi02	X After induction of anesthesia and 3 h after the surgery	Х		
Nosocomial infections recording		Х		
Antibiotics treatment	Х			
Lenght of stay X				
Duration of MV		X		
Mortality	Х			
Adverse events recording	X			

* HLA-DR expression, MDSCs, EV, IL-10, IL-6 and IDO activity will be measured in Rennes.

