8.4 Method of management of missing, unused or invalid data

Missing data will not be replaced. Mixed models can be used in analysis of repeated data.

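### The planned repeated-measures ANOVA of PaO2/FiO2 does not adjust for the ratio before bypass or for centre, so it is valid but less precise than the data allow

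*Combined protocol and SAP*

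**What the plan says.** Section 4.1.2 lists PaO2/FiO2 on day 0 and day 1 as a secondary criterion, and section 3.2 sets the objective of a higher ratio after surgery. Section 4.2.2.3 gives three samples: after induction of anaesthesia (before CPB), 3 h after the end of CPB, and the day after surgery (D1).

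The analysis is in section 8.1.4: "Continuous endpoints repeatedly measured during the study will be compared using a repeated measure two-way (time, group) analysis of variance". Endpoints not measured repeatedly fall under a general rule, "the same strategy as for baseline comparisons will be used", which means a t test or Mann-Whitney test for a continuous variable. Two sentences leave room for more: "For all these analyses, adjustments can be made in case of heterogeneity at inclusion" (section 8.1.4) and "Mixed models can be used in analysis of repeated data" (section 8.4). Neither names a covariate.

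On the design, section 4.3.1 says "Randomization will be stratified per centre". Section 4.2.2.2 says "The patients will be randomized the day of surgery before induction of anesthesia". It gives both arms the same baseline ventilation and separates them only during CPB, when "two settings will be used depending on the study arm".

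**The concern.** A ratio measured in the same patient before the arms differ is likely to predict the ratio afterwards. Used as a covariate, it removes variance from the treatment comparison whether or not the arms look balanced. A rule that adjusts only when heterogeneity is seen gives up that gain in the usual case, and it makes the model depend on the data.

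The plan also leaves two things open. It does not say which samples are levels of time, nor whether the group term or the time-by-group term is the test.

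- **If the pre-CPB ratio is a level of time** (the natural reading, but an inference), the interaction works as a change-type contrast. The group term instead averages in a sample taken before the arms differ.
- **If time covers only 3 h and D1**, the pre-CPB ratio is not used at all.

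On either reading the estimate is less precise than it could be. What is at stake is the precision of one secondary endpoint and a clear statement of its test.

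**Working it through.** **The plan's own figure.** The documents give no power calculation for PaO2/FiO2. The sample size in section 8.2 is for infection at 15% against 10%, two-sided 5%, 80% power. The fixed-sample formula gives (1.960×√(2×0.125×0.875) + 0.842×√(0.15×0.85 + 0.10×0.90))² / 0.05² = 686 per group, or 1372. Applying the three significance levels of section 8.1.3 as nominal p-values, simulation gives 80.1% power at 696 per group. The stated 1392 is therefore reproduced.

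**Inputs.** 700 per arm (1400 patients, equal arms, all contributing) and two-sided 0.05 (section 8.3). Assumed: SD 1 at every time, the same correlation r between every pair of times, r = 0.3, 0.5 or 0.7, and an equal effect at 3 h and D1.

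**Base.** An unadjusted comparison at one time detects (1.960+0.842)×√(2/700) = 0.1498 SD at 80% power. A 2-df test needs noncentrality 9.635 for the same power.

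| Analysis | Detectable difference (SD) | r = 0.3 | r = 0.5 | r = 0.7 |
|---|---|---|---|---|
| Adjusted for pre-CPB ratio, average of 3 h and D1, 1 df | 0.1498×√((1+r)/2 − r²) | 0.112 | 0.106 | 0.090 |
| Group term, 3 h and D1 only, 1 df | 0.1498×√((1+r)/2) | 0.121 | 0.130 | 0.138 |
| Time-by-group interaction, three times, 2 df | √(9.635(1−r)/(350×2/3)) | 0.170 | 0.144 | 0.111 |
| Group term, three times, 1 df | 0.1498×1.5×√((1+2r)/3) | 0.164 | 0.183 | 0.201 |

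The factor 1.5 in the last row arises because an effect present at two of three times averages to two thirds of its size.

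**Like with like.** Part of the gap between the first and third rows is 1 df against 2 df, so adjustment should also be compared at equal df.

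- *1 df:* the variance of the adjusted average divided by that of the contrast (mean postoperative minus pre-CPB) is 0.56/1.05 = 0.53, 0.50/0.75 = 0.67 and 0.36/0.45 = 0.80. At r = 0.9 it is 0.14/0.15 = 0.93.
- *2 df:* the adjusted joint test needs √(9.635(1+r−2r²)/700) = 0.124, 0.117 or 0.100 SD, against 0.170, 0.144 or 0.111 for the interaction. At r = 0.9 it is 0.062 against 0.064.

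The gain over change-type contrasts shrinks as r rises. The gain over unadjusted postoperative comparisons grows.

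**Unequal SDs.** For one postoperative time, change-score variance minus adjusted variance is (SD_pre − r×SD_post)². It is never negative, and is zero only when SD_pre = r×SD_post.

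**Effect at 3 h only.** The adjusted difference at 3 h needs 0.1498×√(1−r²) = 0.143, 0.130 or 0.107 SD. The adjusted average sees half the effect and needs twice its tabled value: 0.224, 0.212 or 0.180 SD. The choice of test therefore depends on the effect expected.

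**Price of adjustment.** Seven centres (section 14) use 6 df and the baseline ratio 1 df, out of about 1398: roughly 0.5% variance inflation. In a null simulation (r = 0.5, assumed centre intraclass correlation 0.05) the type I error was 4.8% for the three-time group term, 5.1% for the change contrast and 5.0% for the adjusted model.

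**The case against.** The strongest reply is that this is a preference about efficiency. The planned ANOVA is valid, the trial is sized for infection, and even the unadjusted analyses detect small standardised effects. No clinically relevant PaO2/FiO2 difference is identified that the plan would miss. That stands, and it keeps the point minor.

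The plan also permits adjustment and mixed models. That is a partial answer only: the permission is optional, names no covariate, and for adjustment waits on heterogeneity. A mixed model with only time and group would have the same weakness.

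Equal SDs and correlations may not hold. Under section 4.2.2.2 the first sample is taken with FiO2 titrated to saturation and PEEP 5–7 cmH2O, while the ICU rule is FiO2 60% and PEEP 5 cmH2O. This stands as a limit on the size of the gain.

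A reader might infer that a covariate measured after randomisation is unsafe. The documents do not support that, because ventilation differs by arm only during CPB. Since only the patient is blinded (section 4.3.2), it does rely on ventilation before CPB following the common settings.

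A reader might also infer that any adjusted test beats any unadjusted one. It does not. At r = 0.3 an adjusted joint 2-df test needs 0.124 SD against 0.121 for the postoperative-only group term. For an effect at 3 h only it needs 0.154 against 0.150 for an unadjusted comparison at 3 h. Adjustment makes each estimate more precise; the choice of test is a separate decision.

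**Conclusion.** The point holds as a minor improvement. The default analysis of PaO2/FiO2 neither adjusts for the pre-CPB ratio nor includes centre, and the optional wording does not supply either. Under the assumptions above, for an equal effect at both postoperative times, the adjusted 1-df average detects 0.112, 0.106 or 0.090 SD. The three candidate readings of the plan need 0.121 to 0.138, 0.170 to 0.111, and 0.164 to 0.201 SD across the same correlations. With an assumed 600 evaluable per arm, every figure is multiplied by √(700/600) = 1.08.

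The direction is secure: against the matching change or unadjusted contrast, adjustment was better at every correlation examined from 0.3 to 0.9. The size is not secure, because the documents give no SD or correlation, and near 0.9 the gain over a change contrast is small. The gain from centre cannot be derived from the documents and is not counted.

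A reader might infer bias, an inflated error rate, or damage to the primary analysis. The documents support none of these: the arms are randomised, and the infection endpoint has its own test and sample size. Nor does the plan state that the pre-CPB ratio is a level of time.

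**What to change.** For PaO2/FiO2, replace the two-way ANOVA in section 8.1.4 with a linear mixed model on the 3 h and D1 ratios, containing arm, time, arm-by-time, the pre-CPB ratio (with its interaction with time) and centre. Make this the planned analysis whether or not heterogeneity is seen at inclusion.

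Name one test in advance. The 1-df adjusted arm effect averaged over the two postoperative times suits a similar effect at both. If the clinical team expects the effect mainly at 3 h, name the adjusted difference at 3 h instead. Report adjusted differences with 95% confidence intervals at each time in either case.

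The same form can serve the other repeated markers that have a D0 value before surgery, so that similar data are analysed alike.

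The cost is one model specification. No extra patients, samples or case report form fields are needed.
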